#### **3.6.2 Laboratory Blood Draws, Safety, and Efficacy Assessments**

Due to the COVID-19 pandemic and the possibility for site closures and/or travel restrictions, clinical laboratory blood draws may be performed by a Home Health Care service provider or by a local laboratory; other safety and efficacy assessments may be performed remotely via phone/audio or video conferencing platforms (with the exception of Facebook).

#### **3.6.3 ECG Assessments**

Due to the COVID-19 pandemic and the possibility for site closures and/or travel restrictions, if Week 6 is a remote visit, ECG assessment may be performed at Week 8 or Week 10.

### **3.6.4 Safety Follow-Up Visit**

Due to the COVID-19 pandemic and the possibility for site closures and/or travel restrictions, the Safety Follow-up visit may be conducted remotely via phone/audio or video conferencing platforms (with the exception of Facebook) per Investigator discretion.

## **4 OUTCOME VARIABLE DEFINITIONS**

### **4.1 Demographic Characteristics**

Demographic characteristics (i.e., sex, ethnic origin, date of birth, and calculated body mass index) will be collected.

### **4.2 Screening, Qualification, and Baseline Characteristics**

Screening:

Inclusion/exclusion criteria, demographic characteristics of age, sex, race, ethnicity, height, weight, body mass index (BMI), medical history, prior and concomitant medications, physical examination, vital signs, adverse events, pregnancy test, 12-lead electrocardiogram (ECG), clinical laboratory results, urine drug screen, alcohol screen, Positive and Negative Syndrome Scale (PANSS), and Columbia-Suicide Severity Rating Scale (C-SSRS) will be collected at screening.

Qualification:

Patients meeting eligibility requirements at the first Screening Visit will undergo an additional in-clinic Qualification Visit during which the following will be collected: eligibility, urine drug screen, alcohol screen, PANSS, C-SSRS, antipsychotic (AP) blood sample, adverse events, and concomitant medications.

Baseline (Day 1 Pre-Dose):

Eligibility, medical history, physical examination, weight, vital signs, 12-lead ECG, pregnancy test, clinical laboratory results, alcohol screen, PANSS, Personal and Social Performance (PSP), Clinical Global Impression-Severity (CGI-S), Schizophrenia Quality of Life Scale (SQLS), C-SSRS, Simpson-Angus Scale (SAS), Abnormal Involuntary Movement Scale (AIMS), and Barnes Akathisia Rating Scale (BARS) will be collected prior to dose administration.

### **4.3 Efficacy Assessments**

The effect of study drug will be evaluated using several validated instruments as described below.

#### **4.3.1 Positive and Negative Syndrome Scale (PANSS)**

The PANSS (Kay et al., 1987) is a psychiatric rating scale designed to measure symptom severity among patients with schizophrenia over the preceding 7 days. The PANSS items are divided into positive, negative and general

psychopathology factors utilizing a 30-item, 7-point rating scheme. Scoring instructions will be provided (to the Rater) with each item accompanied by a complete definition as well as detailed anchoring criteria for all 7 rating points, which represent increasing levels of psychopathology: 1=absent, 2=minimal, 3=mild, 4=moderate, 5=moderate severe, 6=severe and 7= extreme. The PANSS is scored by summation of ratings across items such that the potential ranges are 7 to 49 for each of the Positive and Negative Scales and 16 to 112 for the General Psychopathology Scale. The PANSS total score is the score of all 30 PANSS items taken together.

#### **4.3.2 *Clinical Global Impression-Severity (CGI-S) Score***

The CGI-S rating scale (Guy, 1976) is a commonly used measure of symptom severity and treatment response. The severity scale (CGI-S) is a 7-point scale that requires the clinician to rate the severity of the patient's illness at the time of assessment. CGI-S scores of zero (not assessed) will be treated as missing.

#### **4.3.3 *Personal and Social Performance Scale (PSP)***

The PSP (Morosini et al., 2000) is measure of personal and social functioning of patients with psychiatric disorders. The scale is a hundred-item scale, divided in 10 similar intervals. The score is based on the assessment of a patient's performance in four categories: socially useful activities, personal and social relationships, self-care, disturbing and aggressive behavior.

#### **4.3.4 *Schizophrenia Quality of Life Scale (SQLS)***

The SQLS (Heinrichs et al., 1984) is a self-report Quality of Life scale developed specifically for patients with schizophrenia. It is a 30-item questionnaire comprised of three domains ('psychosocial', 'motivation and energy', and 'symptoms and side-effects').

### **4.4 Efficacy Endpoints**

#### **4.4.1 *Primary Endpoints***

The primary efficacy endpoint will be the change in PANSS total score at Week 12 from Baseline (Day 1, prior to dosing).

#### **4.4.2 *Secondary Endpoints***

The secondary endpoints for this study are:

- Change in CGI-S score at Week 12 from Baseline
- Change in PSP scale score at Week 12 from Baseline

#### **4.4.3 *Exploratory Endpoints***

Exploratory efficacy endpoints are:

- Change in PANSS total score at Weeks 2, 4, 8 and 10 from Baseline
- Change in PANSS Positive Symptoms Factor Score (PSFS; items P1-P7) at Weeks 2, 4, 8, 10, and 12 from Baseline
- Change in PANSS Negative Symptoms Factor Score (NSFS; items N1-N7) at Weeks 2, 4, 8, 10, and 12 from Baseline
- Change in General Psychopathology Symptoms Factor Score (items G1-G16) at Weeks 2, 4, 8, 10 and 12 from baseline
- Change in PANSS Cognitive Symptoms (items P2, N5, G5, G10, G11 at Weeks 2, 4, 8, 10, and 12 from Baseline
- Change in Marder Negative Symptoms Factor Score (Marder NSFS; items N1, N2, N3, N4, N6, G7, G16) at Weeks 2, 4, 8, 10, and 12 from Baseline
- Change in PANSS total score at Week 12 from the average of the Screening, Qualification, and Day 1 pre-dose assessments
- Change in CGI-S score at Weeks 2, 4, 6, 8, and 10 from Baseline
- Change in PSP score at Week 6 from Baseline
- Change in Schizophrenia Quality of Life (SQLS) at Week 12 from Baseline

## 4.5 Safety and Tolerability Assessments

Safety of CTP-692 will be assessed by evaluating adverse events, vital signs, concomitant medications, clinical laboratory parameters including blood urea nitrogen (BUN) and creatinine, urinalysis, ECG results, as well as physical examinations. Extrapyramidal symptoms (EPSs) will be evaluated using SAS, AIMS, and the BARS. Assessment of suicidality will be performed at every visit using the C-SSRS.

### 4.5.1 Adverse Events

An adverse event (AE) is any untoward medical occurrence that may appear or worsen in a patient during the course of a study. It may be a new intercurrent illness, a worsening concomitant illness, an injury, or any concomitant impairment of the patient's health, including laboratory test values, regardless of etiology. Any worsening (i.e., any clinically significant adverse change in the frequency or intensity of a pre-existing condition) will be considered an adverse event.

A worsening of the condition under study will not be considered as an AE.

An AE can be any unfavorable and unintended sign (including a new, clinically important abnormal laboratory finding), symptom, or disease temporally associated with the Study Medication, whether or not it is related to the product.

#### **4.5.2 *Columbia Suicide Severity Rating Scale***

The Columbia Suicide Severity Rating Scale (C-SSRS, Oquendo et al., 2003) is a suicidal ideation rating scale. The scale identifies behaviors and thoughts that are associated with an increased risk of suicidal actions in the future. There are 2 versions of the scale being used in this protocol (Baseline/Screening and Since Last Visit).

#### **4.5.3 *Laboratory Safety Assessments***

Samples for the following laboratory tests will be collected at the time points specified in the Schedule of Assessments (Table 1).

Alcohol breathalyzer:	Assesses ethyl alcohol
Coagulation:	Includes prothrombin time test (PT), partial prothrombin time test (aPTT), international normalized ratio (INR)
Hematology:	Consists of complete blood count, platelet count, white blood cell count with differential
Pregnancy:	Assesses hCG; conducted for females of childbearing potential only
Serum renal parameters:	Includes blood urea nitrogen (BUN), serum creatinine, eGFR
Serology screen:	Includes human immunodeficiency virus antibody (HIV-Ab), hepatitis B surface antigen (HBsAg), hepatitis C virus antibody (HCV-Ab)
Serum chemistry:	Includes alanine aminotransaminase (ALT; SGPT), albumin (ALB), alkaline phosphatase (ALK-P), amylase, aspartate aminotransaminase (AST; SGOT), total bilirubin, direct bilirubin, indirect bilirubin, calcium (Ca), carbon dioxide (CO 2 ), chloride (Cl), total cholesterol, creatine kinase (CK), follicle-stimulating hormone (FSH), gamma-glutamyl transferase (GGT), glucose, lactic dehydrogenase (LDH), lipase, magnesium, total protein, phosphorus, potassium (K), sodium (Na), uric acid
Urinalysis:	Includes bilirubin, glucose, ketones, nitrates, occult blood, protein, specific gravity, urobilinogen, pH, leukocytes, microscopy, creatinine, UACR, urine volume

Urine drug screen:	Includes amphetamines/methamphetamines, barbiturates, benzodiazepines*, cocaine metabolites, methadone, phencyclidine, opiates
--------------------	--

\* Positive test at Week -5 and Week -3 allowed if drug is prescribed by a physician.

#### **4.5.4 Vital Signs**

Resting vital signs, including systolic, diastolic blood pressure, heart rate (measured as pulse), respiratory rate and temperature will be measured after the patient has been in a supine or semi-supine position for at least 5 minutes at the time points specified in the schedule of events (Table 1).

Weight and height will be measured and used to calculate the patient's BMI. Weight and height will be converted as needed to kilograms and centimeters, respectively, prior to statistical analyses.

#### **4.5.5 Electrocardiogram**

Twelve-lead electrocardiograms (ECGs) will be performed after the patient has rested in a supine or semi-supine position for at least 5 minutes. Individual parameters including PR, QT, QTcF, QRS, and RR intervals will be collected. Repeat electrocardiograms (if deemed necessary) should be performed at least 5 minutes apart. ECG will be performed at Screening, Baseline, Week 6, and Week 12; if Week 6 visit is a remote visit, ECG assessment may be performed at Week 8 or 10.

#### **4.5.6 Physical Examination**

A full physical examination will be performed at Screening, Baseline, and Week 12. It will include an examination of all major organ systems. Brief physical examinations will be symptom-directed and performed at Weeks 2, 4, 6, 8, 10, and 13 (follow-up); the Week 13 brief physical exam will be conducted if the visit occurs in-clinic.

### **4.6 Extrapyramidal Symptoms**

#### **4.6.1 Simpson-Angus Scale (SAS)**

The SAS consists of a list of 10 symptoms of parkinsonism (gait, arm dropping, shoulder shaking, elbow rigidity, wrist rigidity, head rotation, glabella tap, tremor, salivation, and akathisia). Each item is rated on a 5-point scale, with a score of one representing absence of symptoms, and a score of 5 representing a severe condition. The SAS total score is the sum of the scores for all 10 items.

#### **4.6.2 Abnormal Involuntary Movement Scale (AIMS)**

The Abnormal Involuntary Movement Scale (AIMS) is a 10-item clinician-rated scale to assess severity of dyskinesias (specifically, orofacial movements and extremity and truncal movements) in patients taking neuroleptic medications. Body areas of interest include Facial and Oral, Extremities and Lower, and

Trunk. Each item is scored on an ordinal scale that ranges from 0 to 4: none, minimal, mild, moderate, or severe. Additional global items assess the overall severity, tardive dyskinesia-associated functional impairment, and the patient's level of awareness of the movements and distress associated with them.

#### **4.6.3 Barnes Akathisia Rating Scale (BARS)**

The Barnes Akathisia Rating Scale (BARS) consists of 4 items related to akathisia: objective observation of akathisia by the Investigator, subjective feelings of restlessness by the patient, patient distress due to akathisia, and global evaluation of akathisia. The first 3 items are rated on a 4-point scale, with a score of 0 representing absence of symptoms and a score of 3 representing a severe condition. The global clinical evaluation is made on a 6-point scale, with 0 representing absence of symptoms and a score of 5 representing severe akathisia. To complete this scale, patients are observed while they were seated and then standing for a minimum of 2 minutes in each position. Symptoms observed in other situations (e.g., while engaged in neutral conversation or engaged in activity on the ward) are also rated. Subjective phenomena are to be elicited by direct questioning.

### **4.7 Antipsychotic (AP) Medication Blood Level**

Blood samples will be taken to assess blood levels of the AP medication being taken by the patient. The confirmation of levels of one of the AP medications listed in APPENDIX A of the protocol will be required for patients to be eligible for randomization to the Treatment Period.

### **4.8 CTP-692 Blood Level**

CTP-692 blood levels will be analyzed and reported separately by the bioanalytical laboratory. Times of blood draws relative to dosing of Study Medication will be provided in a listing.

### **4.9 Concomitant Medications**

Concomitant medications will be reviewed and documented each visit during the study and are defined as any medications received at or after the first dose of study medication, medication that was received before initial dosing and continued after initial dosing of study medication, or medication with missing stop date.

### **4.10 Prior Medications**

Prior medications are any medications that ended before the first dose of study medication.

## **5 STATISTICAL ANALYSES**

Statistical analyses will be performed using SAS® software version 9.4.

## **5.1 Statistical Methodology**

### **5.1.1 Sample Size Determination**

Approximately 75 patients will be randomized to each treatment arm to achieve a sample size of approximately 60 patients per arm who complete the study. A sample size of 60 per arm provides at least 80% power for the change at Week 12 from Baseline in PANSS total score, assuming a treatment difference from placebo of 5.2 and standard deviation of 10, on a two-sided t-test at 0.05 significance level.

### **5.1.2 Populations for Statistical Analysis**

#### **5.1.2.1 Safety Population**

The Safety Population (SP) includes all patients who receive at least one dose of study medication.

#### **5.1.2.2 Efficacy Population**

The Efficacy Population (EP) will include all patients who receive Study Medication and have at least one post-baseline PANSS assessment during the Treatment Period.

#### **5.1.2.3 Efficacy Population – COVID Related**

Due to the pandemic during the conduct of the trial, a COVID-related Efficacy Population (COVID-EP) will also be identified. COVID-EP will be defined as all patients who receive study medication and have at least one post-baseline PANSS assessment during the Treatment Period and have not discontinued from the study or had a dose interruption due to direct COVID-related events. The COVID-related Efficacy Population will be identified prior to database lock and will exclude individuals who contracted the virus, had clinic access restricted due to COVID conditions, etc.

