#### **5.1.2.4 Per-Protocol Population**

The Per Protocol analysis population (PP) will include all patients in the Efficacy Population who were dosed according to protocol with no major protocol deviations with respect to eligibility criteria and efficacy assessments, and will be finalized prior to database lock.

The full set of efficacy analyses will be conducted for the EP and COVID-EP, whereas analyses for the PP analysis population will be restricted to the change in PANSS Total Score at weeks 2, 4, 8, 10, and 12.

Individual assignment to each analysis population will be provided in a listing.

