#### **5.1.4 Procedures for Handling Missing Data**

In general, missing data will not be imputed, as the Mixed Model Repeated Measures (primary analysis approach) is considered valid under a Missing at Random (MAR) missingness mechanism.

As a sensitivity analysis for the primary endpoint, the last observation carried forward (LOCF) method will be used to impute missing values for patients who withdraw from the study prior to the completion of the 12-week Treatment Period.

A listing will be provided indicating patients and visits with missing data or remote visits due to COVID-19, as well as early terminations due to COVID-19.

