## 5.3 Patient Disposition

The number and percentage of patients in each treatment group will be summarized for each investigative site (and combined) for each analysis population. The number and percentage of patients who are randomized, treated, prematurely discontinued (overall and by reason), and who complete the study will be summarized. The frequency and percentage of patients who withdraw or discontinue from the study, along with the reason for withdrawal or discontinuation, will be summarized by treatment. Individual patient dispositions will be provided by a listing.

All reported major protocol deviations and determined exclusions from any analysis population(s) will be provided in a listing.

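### Does the COVID-related Efficacy Population need a closed exclusion list, and censoring in place of removing whole patients?

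*SAP*

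**What the plan says.** SAP 5.1.2.2 defines the EP as treated patients who "have at least one post-baseline PANSS assessment during the Treatment Period". SAP 5.1.2.3 then says that a COVID-EP will also be identified. Its defining sentence takes EP-type patients who "have not discontinued from the study or had a dose interruption due to direct COVID-related events". A further sentence says that the set will be "identified prior to database lock and will exclude individuals who contracted the virus, had clinic access restricted due to COVID conditions, etc".

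SAP 5.1.2.4 gives the set a substantial role: "The full set of efficacy analyses will be conducted for the EP and COVID-EP". The Per-Protocol population, by contrast, is analysed for PANSS total score only. The same section adds that "Individual assignment to each analysis population will be provided in a listing", and SAP 5.3 that "determined exclusions from any analysis population(s) will be provided in a listing".

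On missing values, SAP 5.1.4 does not impute, because the MMRM "is considered valid under a Missing at Random (MAR) missingness mechanism". It also promises a listing of "patients and visits with missing data or remote visits due to COVID-19, as well as early terminations due to COVID-19". SAP 3.6 treats remote assessments the same as on-site ones and pools them for analysis. Footnote 10 of the SAP schedule of assessments allows study drug to be sent to the patient.

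**The concern.** Two features invite criticism.

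First, the two sentences of SAP 5.1.2.3 differ in breadth. The defining sentence needs a discontinuation or a dose interruption. The later one names infection and restricted clinic access, and leaves the list unfinished. It may illustrate the first sentence or widen it. A completer who received drug by post, missed no dose and was rated by video stays in on the narrow reading and may go out on the wide one. The protocol defines no COVID population, so it does not settle the matter.

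Second, the unit of removal is the patient. Someone infected in Week 9 loses the Week 2, 4 and 8 PANSS scores as well, although the MMRM can use an incomplete profile under MAR. Discontinuation and dose interruption occur after randomisation, so removing whole patients for them gives up precision and, in principle, comparability of the arms. Because the COVID-EP carries the full set of efficacy analyses, its size and precision depend on a definition that two analysts could apply differently.

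**Working it through.** **The plan's own figure.** SAP 5.1.1 gives 60 completers per arm, difference 5.2, SD 10, two-sided 0.05. The standard error is 10 × √(2/60) = 1.826. Power is 0.806 by the noncentral t distribution and 0.813 by the normal approximation, so the stated 80% or more reproduces.

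**Inputs for the comparison.** From the documents: 75 randomised and 60 completing per arm (20% dropout), SD 10 at Week 12, PANSS at Weeks 2, 4, 8, 10 and 12. Assumed, because the documents are silent: share affected 5%, 10% or 20%; correlation 0.80 to 0.90 per two weeks; dropout times and COVID event times each uniform over 12 weeks, and independent of each other and of outcome.

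**Formulas.** With V the covariance of the five visits, and p_S the share of patients observed at the visits in S, the information per arm is I = Σ 75 × p_S × V_S⁻¹, each term placed in the rows and columns of S. The variance of the Week 12 difference is 2 × [I⁻¹] at Week 12. Removing a share x of patients gives variance/(1 − x). Censoring keeps each affected patient's visits before the earlier of event and dropout. The mean number of PANSS visits before the event is (0×2 + 1×2 + 2×4 + 3×2 + 4×2)/12 = 2.0 of 5. Power is Φ(5.2/SE − 1.96).

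**Results.** With nobody removed or censored, the EP standard error is 1.775 (correlation 0.80) or 1.737 (0.90), and power is 83.4% to 85.0%.

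| Share affected | SE rise, removal | SE rise, censoring | Power, removal | Power, censoring |
|---|---|---|---|---|
| 5% | 2.6% | 1.5–2.0% | 81.5–83.1% | 81.9–83.9% |
| 10% | 5.4% | 3.1–4.1% | 79.4–81.1% | 80.3–82.8% |
| 20% | 11.8% | 6.6–8.9% | 74.6–76.4% | 76.8–80.2% |

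The 95% half-width is 1.96 × SE. At 10% affected it is 3.67 with removal and 3.62 with censoring at correlation 0.80, and 3.59 and 3.51 at 0.90: a gain of 0.05 to 0.08 PANSS points. At 20% the gain is 0.10 to 0.18 points.

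A second calculation used compound symmetry of 0.5 or 0.7, or correlation 0.80 per two weeks, with dropout of 5% after each of Weeks 2, 4, 8 and 10. It gave power of 0.80–0.82 with removal and 0.81–0.84 with censoring at 10%, and 0.75–0.77 against 0.77–0.81 at 20%.

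**If every affected patient is a COVID discontinuer.** Removal raises the SE by 0.7–1.2% at 5% and 1.4–2.4% at 10%. Censoring costs about nothing, because the pre-event scores are already all, or nearly all, that the EP has for these patients. It therefore also tells the reader almost nothing beyond the EP analysis.

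**Restricted access alone.** Setting two consecutive remote PANSS visits to missing raises the SE by 0.6–0.9% at 10% affected, against 5.4% with removal. This depends on the length of the remote spell: if all five visits are remote, the two options coincide.

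**Reading the definition.** SAP 3.6 treats remote ratings as equivalent to on-site ones. Removing a fully dosed, remotely rated completer fits poorly with that rule, so the narrower reading is the more natural one. On that reading, infection and restricted access are examples of what may cause a discontinuation or interruption.

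**The case for a change.** The best case for a change is that listings show who was removed without supplying the rule, and that a set with the full efficacy analyses deserves a reproducible one. Closing the list would cost a line of SAP text. That is fair as tidiness, and the ambiguity is real.

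There is also a bias argument. In a simulation with no treatment effect and equal event rates by arm, events after Week 4 were made to depend on the Week 4 score in the active arm only. Removing patients shifted the Week 12 difference by 0.3 to 0.5 points at 10% affected and 0.6 to 0.9 at 20%. A MAR analysis that kept the earlier visits stayed within about 0.05. This shows what could happen under an adverse assumption. Nothing in the documents suggests that COVID events would track PANSS in one arm only, and the EP analysis, which removes nobody for COVID, stands beside the COVID-EP for comparison.

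It is also true that the SAP never labels the EP as primary. However, the EP comes first, and the COVID-EP is introduced as an extra set built on the same criteria.

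Censoring has costs of its own. It estimates a hypothetical effect without COVID events, under MAR, and no longer describes patients whom COVID did not touch. It discards observed scores after a brief interruption with resumed dosing. It needs a dated event for each affected patient. A version that sets remote ratings to missing would depart from SAP 3.6.

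**Conclusion.** No change is needed. The open-ended list is missing detail. The team must resolve it to fix membership before lock, SAP 3.6 points to the sensible reading, and the assignments and exclusions will be visible in listings. No pre-event score is lost to the trial, since each enters the EP analysis. Its absence from the COVID-EP is what a patient-level subset means, as with the Per-Protocol population.

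Removal against censoring is a fair trade-off between two supplementary analyses that answer different questions. The precision at stake is 0.05 to 0.08 PANSS points of half-width and about 1 to 2 points of power at 10% affected, or 0.10 to 0.18 points of half-width and about 2 to 4 points of power at 20%. These sizes rest on assumed shares and correlations, and on event times unrelated to outcome. Whatever those values are, the EP result and the sample-size justification are unaffected.
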